Inclusion Criteria	Agree to participate in the study, and the legal representative voluntarily signs the informed consent form Children and adolescents aged 6-18 with typical development, regardless of gender

Exclusion criteria	Except for flat feet, there are other congenital deformities of the lower limbs or spine that affect foot posture. In addition to flat feet, there are other muscle, nerve, and bone diseases that affect foot posture. The researchers have determined that they are not suitable to participate in this study
Effectiveness analysis	Main efficacy indicators: Motional foot posture improvement (push off phase foot flip angle) Secondary efficacy indicators: Static foot posture improvement (foot posture index FPI-6)
Security analysis	The detection equipment and methods used in this study mainly include harmless optical motion capture, structured light 3D scanning, wearable sensors, and bioelectrical resistance body composition analysis; X-ray, bone age, ultrasound and other imaging tests are all operated by professional technicians, and the collection environment and methods meet safety requirements; The intervention method is non pharmacological therapy, which is harmless to the human body; The data acquisition and analysis process strictly follows privacy protection regulations, and there is no security risks.
statistical analysis	Analysis set: Use the full analysis set for statistical analysis. Full analysis set (FAS): Includes all enrolled subjects who have received at least one non pharmacological intervention and have measurable baseline foot injury. Sample size determination: According to epidemiological surveys, the incidence of foot pain events in children is about 12%, and it is determined based on similar studies. Statistical analysis: SPSS 25.0 statistical analysis software will be used for statistical analysis
follow-up	Feedback on foot pain events; Execution of martial arts training and vertical rhythm training; The efficacy and adverse reactions of martial arts training and vertical rhythm training.
Statistical methods	The method used is independent sample t-test to analyze gait parameters of normal and poor foot postures, and repeated measures ANOVA to analyze gait and foot posture parameters before and after intervention.

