Expected progress	Starting from January 2024 to December 2024, recruit phase one participants and initiate the study Screening of Phase II subjects and conducting experiments from January 2025 to December 2025

	Screening of Phase III subjects and conducting experiments from January 2026 to December 2027
--	---

List of abbreviations and definitions of terms

abbreviation	definition
WBV	Whole Body Vibration Training: The subject is placed on a vibration platform that provides vertical sinusoidal vibrations to the body, stimulating receptors and causing neuromuscular excitation.
IMU	Inertial Measurement Unit: including gyroscope and accelerometer.

Experimental Procedure Table

project	baseline	Phase I		Phase II	Phase III
		Asymptomatic	Foot pain intervention		
informed consent	✓	✓	✓	✓	✓
Inclusion/exclusion criteria	✓	✓	✓	✓	✓
physical examination	✓	✓	✓	✓	✓
Foot pain VAS score	✓	✓	✓		
All-weather sensors		✓	✓		
WBV Training			✓		
TCM training			✓		
3D foot scan		✓	✓	✓	✓
Foot X-ray in weight-bearing position				✓	
Analysis of Traditional Chinese Medicine Tongue Images				✓	
Body fat measurement				✓	
Saliva gene analysis				✓	
Wrist bone age				✓	
Bone density ultrasound				✓	
Magnetic resonance imaging scan					✓
Gait optical action capture					✓
Surface electromyography collection					✓
Foot pressure test					✓

1. Research background

1.1 research meaning

Foot injury is one of the most common motor system diseases in children, and the most common clinical manifestation is foot pain. At present, there are few reports on the incidence of foot pain in Chinese children. Foreign studies have shown that the incidence of foot pain in children and adolescents is as high as 10% -15%, accompanied by the risk of foot injury and foot deformity. Our preliminary research found the same pattern, with the highest proportion of foot pain among children aged 6-11 in Foshan reaching 12.67%, and the proportion of foot pain gradually increases with age. Among young people who frequently suffer from ankle sprains, about 25% have long-term ankle instability, making ankle injuries a common disease among adolescents and children.

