In recent years, the implementation of the "double reduction" policy has encouraged children to increase their physical activity, with the aim of enhancing their physical fitness. However, due to inadequate prevention and control measures, there have been more cases of ankle injuries in children in clinical practice. There are 250 million children in China, and the estimated total number of foot injuries is 20-30 million. As age increases, the risk of foot injury and its complications increases, with approximately 24% of adults having experienced foot injury or foot disease [3,4]. The underdevelopment of children's feet, abnormal foot shape, and uneven lower limb force lines are important structural causes of foot injuries in children. As a result, abnormal foot movement posture is the dynamic cause of foot injuries. Failure to correct abnormal foot movement posture in a timely manner after causing foot injury will further lead to multi joint posture abnormalities, causing a vicious cycle of secondary injury, ultimately affecting limb and trunk force lines, and causing damage to knee joints, hip joints, and spine [5,6]. Partial injuries can cause serious consequences, such as cartilage damage to the talus, and may even lead to talus necrosis, endangering children's health [7]. Early detection and intervention of foot injuries in children are important tasks to ensure their healthy development.

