Abnormal arch development can lead to flat feet and other deformities in children [17], posing a threat to their health. Some patients may persist into adolescence and adulthood. Foreign studies have shown that flat feet are a common foot deformity in children, mainly characterized by the collapse or flattening of the medial longitudinal arch (MLA) of the foot, usually accompanied by abduction of the forefoot, inversion of the midfoot, eversion of the hindfoot, abduction of the tarsal joint, and eversion of the subtalar joint. Due to factors such as urbanization, premature/inappropriate shoe wearing, overweight/obesity, excessive/insufficient exercise, and excessive joint laxity, the risk of developing flat feet increases [18,19]. According to the impact of age on flatfoot in foreign children, it is estimated that approximately 45% of preschool children and 15% of older children (with an average age of 10 years) suffer from flatfoot [20]. There are significant differences in the estimated prevalence of flatfoot among foreign epidemiology, ranging from 0.6-77.9% [20]. Although there are different estimates of the prevalence of flatfoot in children. There is a consensus that the incidence of flatfoot disease is inversely proportional to the age of children. The overall incidence of flat feet among 3226 children aged 7-12 in Shanghai, China is 56.1%, and the incidence gradually decreases with age [21]. The detection rate of flat feet is still 13% even at the age of 12. Lin et al. used a gait analysis system to study 377 children aged 2-6 years. The detection rates of moderate flat feet were 43%, 31%, 24%, and 19%, respectively; The detection rates of severe flat feet are 14%, 9%, 4%, and 2%, respectively.

The hazards of poor foot posture and foot pain

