All subjects are required to complete screening period related examinations before enrollment and be screened according to inclusion and exclusion criteria.

- 1) Sign informed consent form
- 2) Record demographic data: date of birth, gender, initials;
- 3) Anthropometry: including height, weight, and length of both lower limbs
 - ① Measurement of length of both lower limbs

Measurement position: supine position, lower limbs extended, pelvis in neutral position, hip joint in neutral position.

Measurement method: Use a soft tape to measure the shortest distance from the anterior superior iliac spine to the medial malleolus, measure the left and right legs separately, and record the results in the test registration form.

- ② height

Measurement method: The subject stands barefoot in a "upright" position, with their heels, sacrum, and shoulder blades tightly against the wall. The measurer can stand on either side of the person being measured, adjust their head to the lowest point between the upper edge of the tragus and the lower edge of the eye socket, and start the height measuring device to measure their height.

Measurement requirements: The height should be measured barefoot each time, using the same measuring instrument at the same time (more accurately in the morning), with the same person measuring as much as possible, and the body posture should be consistent before and after. Each measurement of height requires two consecutive measurements with a 30 second interval. The results of the two measurements should be roughly the same, and the error in height should not exceed 0.5 centimeters.

- ③ weight

Testing method: Wear lightweight clothing, stand barefoot, naturally on an electronic weight scale, measure weight twice in a row with a 30 second interval. The results of the two measurements should be roughly the same, and the error in weight should not exceed 0.5KG.

4) Facial VAS score for foot pain

The subjects represent the degree of foot pain by selecting the corresponding pattern on the scale.

[figure not shown]

Figure 1 Facial VAS score for children: representing foot pain by selecting the corresponding pattern on the scale degree

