7.2 Phase One

We plan to recruit 1000 participants aged 6-18 to record their basic health status and static foot posture at baseline. Subsequently, sensors were used to collect gait data for more than 8 hours per day for the next 4 weeks, and all enrolled children wore wearable sensors in their daily lives. The obtained data is uploaded to the cloud server through a mobile application, and remote monitoring and daily event recording are achieved by uploading the data through the APP. When subjects experience foot pain events, they should promptly report to the researchers through the APP. After determining foot pain based on VAS scores, the subjects with foot pain will be enrolled in the observation group, exercise intervention group, and WBV intervention group according to their wishes. Children in the observation group should rest according to medical advice and not participate in sports activities. Children in the intervention group received WBV vertical rhythm or exercise training programs under the guidance of researchers' follow-up. The follow-up time is once a week, and the training lasts for a total of 4 weeks. Using a self-developed app for researchers to remotely monitor and guide children's training movements, and track training progress.

The device uses Huawei S-TAG foot rings, matched with HarmonyOS 2+/Android 6.0+/iOS 9.0+systems; IP68 (GB/T 4208-2017), waterproof rating of 50 meters; Bluetooth: BT 5.0 transmits data; Running Scene

Battery life: Run for 1 hour per day, run 5 days a week, leave it still when not in use, and have a battery life of 30 days.

(1) WBV Vertical Rhythm Training Standard Process: Children enrolled in the study will be trained at home using vertical rhythm equipment under the guidance of researchers and parental supervision. WBV training lasts for 4 weeks, five days a week, with 15 minutes of training per day. Each movement lasts for 30 seconds, and there is a 30 second break between groups.

(2) Standard process for traditional Chinese medicine exercise training: Children enrolled in the group will undergo exercise training under the supervision of their parents, following the teaching of a self-developed APP. The Yi Jin Jing training will last for 4 weeks, five days a week, with 15 minutes of training per day. There will be a total of 12 exercises, each lasting 1 minute, with a 15 second break between groups.

Figure 2 S-TAG Wearable Sensor

7.3 Phase 2

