13.2 Definition and selection of analysis set

Use the full analysis set for statistical analysis. Full analysis set (FAS): Includes all enrolled subjects who have received at least one non pharmacological intervention and have measurable baseline foot injury.

13.3 statistical method

Independent sample t-test was used to compare gait parameters between children with foot pain and those without symptoms, while repeated measures ANOVA was used to compare dynamic and static foot posture parameters before and after training intervention.

13.4 Statistical software and general requirements:

- All statistical analyses were conducted using SPSS 25.0 (or higher version).
- Measurement data is described using mean, standard deviation, median, maximum, and minimum values
- Count data is described using frequency and percentage

14. Experimental management

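### The gait comparison between children with and without foot pain (Section 13.3) is an unadjusted t-test pooled over ages 6-18, although the protocol's own background ties age to both foot pain and foot form; age can bias it in either direction.

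*Protocol*

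**What the plan says.** Section 13.3 names one method for relating gait to foot pain: "Independent sample t-test was used to compare gait parameters between children with foot pain and those without symptoms". The synopsis gives the same test for a different contrast, also without adjustment: "independent sample t-test to analyze gait parameters of normal and poor foot postures". Neither place names a covariate, an age stratum or matching.

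The cohort is wide in age. Section 7.2 states: "We plan to recruit 1000 participants aged 6-18 to record their basic health status and static foot posture at baseline". Section 13.1 expects about 12% of these children, about 120, to report foot pain.

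The background sections connect age with both sides of the comparison:

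- **Grouping variable.** Section 1.1 says that "the proportion of foot pain gradually increases with age", directly after a figure for children aged 6-11. It adds more generally: "As age increases, the risk of foot injury and its complications increases".
- **Foot form and gait.** Section 1.2 reports a consensus that "the incidence of flatfoot disease is inversely proportional to the age of children", and Section 1.1 says gait comes close to the adult pattern at about age 7, which lies inside the enrolled range.

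The variables needed for adjustment are collected. Section 7.1 records date of birth and gender, and "Anthropometry: including height, weight, and length of both lower limbs".

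**The concern.** A variable related to both the grouping and the outcome confounds an unadjusted comparison. On the protocol's own account, age is related to the grouping (pain or no pain) and plausibly to the outcome (gait parameters). If children with pain are older on average, the t-test estimates the pain-related difference at a given age plus the gait difference that comes from being older, and it cannot separate the two.

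This is a named method that cannot hold a covariate, so it is not a detail left open for a later analysis plan. A plan that adjusted for age would have to replace it. At stake is the only stated test of whether gait differs between children with and without foot pain. A reported difference could be partly or wholly due to age, and a real one could be understated or overstated.

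**Working it through.** **Inputs from the protocol.** 1000 children aged 6-18 (Section 7.2); 12% with foot pain, so about 120 with and 880 without (Section 13.1); two-sided α = 0.05, which Section 13.1 states for the intervention comparison and which is used here. The protocol gives no sample size, expected difference or age slope for the gait-pain t-test, so there is no figure of its own to reproduce.

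**Assumptions (not in the documents).** Age uniform on 6-18, so variance 12²/12 = 12 and SD 3.464 years. Pain risk linear in age, averaging 12%, with three gradients: 10% to 14%, 8% to 16% and 6% to 18%. Correlation r of the gait parameter with age of magnitude 0.3 to 0.5, of either sign.

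**Step 1: age gap between groups.** Gap = slope × Var(age) / [P(1 − P)], with P(1 − P) = 0.12 × 0.88 = 0.1056.

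- 10% to 14%: (0.04/12) × 12 / 0.1056 = 0.38 years = 0.109 SD of age
- 8% to 16%: (0.08/12) × 12 / 0.1056 = 0.76 years = 0.219 SD
- 6% to 18%: (0.12/12) × 12 / 0.1056 = 1.14 years = 0.328 SD

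**Step 2: bias and false-positive rate.** Bias in SD of the gait parameter = |r| × gap in SD of age. Standard error of the crude difference = √(1/120 + 1/880) = 0.0973 SD. With z = bias / 0.0973, the rejection rate when there is no difference at a given age is Φ(z − 1.96) + Φ(−z − 1.96).

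| Pain risk, age 6 to 18 | \|r\| | Bias (SD) | z | Type I error |
|---|---|---|---|---|
| 10% to 14% | 0.3 | 0.033 | 0.34 | 6% |
| 10% to 14% | 0.5 | 0.055 | 0.56 | 9% |
| 8% to 16% | 0.3 | 0.066 | 0.67 | 10% |
| 8% to 16% | 0.5 | 0.109 | 1.12 | 20% |
| 6% to 18% | 0.3 | 0.098 | 1.01 | 17% |
| 6% to 18% | 0.5 | 0.164 | 1.69 | 39% |

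**Step 3: effect on a real difference.** Take a true difference of 0.3 SD at a given age (assumed). Without bias, power is about 87%. If age works against the difference, the crude expectation falls to 0.3 − 0.033 = 0.27 SD in the mildest case and 0.3 − 0.164 = 0.14 SD in the strongest, and power falls to 78% and 29%. If age works with it, the expectation rises to 0.33 and 0.46 SD, an overstatement. The sign reverses only when the true difference is smaller than the bias.

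**Step 4: check by simulation.** 1500 simulated trials of 1000 children per scenario, same pain gradients, gait falling by 0.05 to 0.20 residual SD per year (|r| = 0.17 to 0.57, a wider range than above). With no true difference, the t-test rejected in 6-9%, 6-25% and 9-49% of trials for the three gradients. A linear model with age as covariate rejected in 4.5-6.3%, and with a true 0.3 SD difference it recovered 0.30 on average.

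**The case against.** **The size rests on assumption.** This stands. No gait-age slope and no age-specific pain rates across 6-18 are given. In the mildest row above the type I error is 6%, which would do little harm.

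**The age trends are narrower than the comparison.** This partly stands. The rise of foot pain with age follows a sample aged 6-11; the broader statement in Section 1.1 concerns injury and its complications. The fall with age concerns static flatfoot, whereas the sensor measure in Section 8.1 is a dynamic push-off angle. Section 1.1 has gait near adult form at about 7, and Section 1.2 has arch development stopping at 13-14, so a steady trend over the whole range is not stated. These points limit the size and favour a non-linear age term. They do not make the groups comparable in age.

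**Direction.** A reader might infer from Section 1.1 that children with pain are expected to show more valgus, so that age must mask or reverse the signal. The text does not support this: it reports a significant difference in the valgus angle and gives no sign. Age could equally inflate the contrast.

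**The warning model.** A reader might also infer that the t-test selects features for the warning model. No section says so. The model is to be built with neural networks on sensor data, separately from Section 13.3, and a feature that carries age information may still predict validly.

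**Importance.** The main efficacy indicator (Section 8.1) is analysed by repeated measures ANOVA, and the sample size in Section 13.1 rests on the intervention comparison. Neither depends on this t-test. That stands and limits the severity.

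**Conclusion.** The point holds. Section 13.3 fixes an unadjusted comparison in a cohort where, by the protocol's own background, age is related to the grouping and plausibly to the outcome. The contrast is open to age bias in either direction. Under the stated assumptions (uniform age, linear pain gradient from 10%-14% up to 6%-18%, gait-age correlation 0.3 to 0.5 in magnitude), the bias is about 0.03 to 0.16 SD and the type I error about 6% to 39% against a nominal 5%.

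Confidence is high that the method is open to this bias and only moderate about its size. It should be fixed, as a weakness in a supporting observational comparison; it is not a fault in the main efficacy analysis or in the fitting of the warning model.

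**What to change.** In Section 13.3, replace the independent-sample t-test for the gait-pain comparison with a linear model of each gait parameter on pain status, adjusted at least for age (allowing non-linearity, for example by age bands or a spline) and sex. Add height and weight as a further or sensitivity adjustment. The t-test may remain as a crude descriptive comparison, labelled as such. Bring the synopsis wording into line, since it names a different contrast for the same test.

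The cost is a sentence or two in the protocol. Date of birth, gender, height and weight are already recorded at screening (Section 7.1), and SPSS, the named software, fits the model. No further children, visits or measurements are needed.

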prevent the occurrence of injuries in advance. It is even more difficult to control the risk of foot injuries and rehabilitation processes in large-scale children. Therefore, we used Huawei HUAWEI S-TAG inertial sensors to observe the foot posture characteristics of children with foot injuries in the early stage. In the study, it was found that the static and dynamic foot posture of children are closely related to foot pain, mainly due to the significant difference in the angle of calcaneus valgus and the swing angle of the longitudinal axis of the foot during gait (toe push off phase) between normal children and children with foot pain. Based on the above, this project focuses on the research of neural network models for key rehabilitation nodes in the core content of foot injury risk prediction, WBV intervention process, and exercise intervention process. Inertial sensors are used to observe foot posture data 24/7, and regular features in gait before injury and during rehabilitation process are mined. Neural network algorithms are used to construct algorithm models, and recognition and evaluation models are established for earlier "compensated", "decompensated", and "key rehabilitation node" gaits before injury. Prompt for decompensated gait before injury occurs, thereby achieving early warning and monitoring of the rehabilitation process before injury occurs. The prediction accuracy of this model approaches the real world infinitely as the amount of training data continues to increase.

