5.4 Exit criteria

All enrolled subjects have the right to withdraw from this study at any time.

Participants who withdraw from the study for any reason must record their reasons, including the following:

- 1) The subject withdraws the informed consent form;
- 2) Subject lost to follow-up;
- 3) The legal representative of the subject refuses to continue the follow-up visit;
- 4) The researchers believe that for other reasons, the subjects are not suitable to continue participating in this study;

Participants who withdraw from the study midway are considered dropout samples. When the subject falls off, efforts should be made to obtain as much as possible contact, complete the evaluation project, and fill out the research summary page.

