13.1 Sample size determination

This study is divided into three stages: the first stage is a prospective intervention study, and the second and third stages are observational studies. The sample size of the experiment is mainly based on the requirements of the first stage research, calculated using PASS 15.0 software. Compare the differences in dynamic and static foot posture between the intervention group and the observation group for subjects with foot pain after 4 weeks of intervention. Require bilateral testing, with $\alpha=0.05$, $\beta=0.1$, and a confidence (testing efficiency) of $1-\beta=90\%$. The expected difference in effect between the intervention group and the observation group is 0.8, so each group requires 34 people, for a total of 102 people in the three groups. According to the preliminary epidemiological investigation, the incidence of foot pain events in children is about 12%. The planned recruitment sample size is 1000 people, which can collect about 120 cases of foot pain events, meeting the sample size requirements.

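### Before/after repeated measures ANOVA leaves out children with no after-intervention value, although the full analysis set includes them, so the efficacy comparison becomes a completers analysis

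*Protocol*

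**What the plan says.** Section 13.2 of the protocol names the full analysis set as the basis for analysis. The set "Includes all enrolled subjects who have received at least one non pharmacological intervention" and also requires a measurable baseline. It does not require a measurement after baseline.

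Section 13.3 fixes the method: "repeated measures ANOVA was used to compare dynamic and static foot posture parameters before and after training intervention". Section 13.4 names SPSS 25.0 or later. Section 8.1 defines the main efficacy indicator, the push-off angle from the wearable sensor, as the after value compared with the before value. FPI-6 in section 8.2 is the secondary indicator, and the protocol schedules no FPI-6 measurement within the training weeks.

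Section 5.4 foresees loss: "Participants who withdraw from the study midway are considered dropout samples". It also asks staff to try to reach these children and finish their evaluation.

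On sensor data during training, the protocol points both ways. The Experimental Procedure Table ticks the all-weather sensor under foot pain intervention, and section 1.1 says that "regular features in gait before injury and during rehabilitation process are mined". Section 3.1 allows gait collection to stop once foot pain has been reported, and section 7.2 describes sensor wear for the four weeks after baseline, ahead of the training steps.

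**The concern.** The population and the method do not fit each other. A child with a baseline and one training session belongs to the full analysis set. Without an after value, that child cannot enter a classical before/after repeated measures ANOVA. Run that way, the analysis labelled full analysis set would be an analysis of children who finished.

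This matters because loss may be unequal. Training is done at home for 15 minutes a day, five days a week, for four weeks, while the observation group is asked to rest. Groups are chosen by the children and are not blinded (sections 4.2.1 and 4.2.2). If children who train without improving are the ones who leave, those who remain make training look better than it is. That pattern is plausible, but it is an assumption and not a figure in the protocol.

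**Working it through.** **The plan's own figure.** Section 13.1 gives alpha 0.05, two-sided testing ("Require bilateral testing"), 90% power, and: "The expected difference in effect between the intervention group and the observation group is 0.8, so each group requires 34 people". No unit or SD is given, so 0.8 is read as a standardised difference. The noncentral t test for two groups gives 90.2% power at 34 per group and 89.3% at 33. The stated 34 is therefore reproduced, and so is 3 × 34 = 102 ("for a total of 102 people in the three groups"). The sample size is not in error.

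**What the named method does.** With two groups and two time points, the group-by-time test equals a t test on change (after minus before). Change exists only for children with both values, so an effective n of 34 needs 34 completers per group.

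**Room for loss.** 12% of 1,000 is 120 expected cases ("which can collect about 120 cases of foot pain events, meeting the sample size requirements"), or 18 more than 102. The loss this absorbs is 1 − 102/120 = 15%, and only if the three self-chosen groups are equal. Power on completers, for assumed loss rates:

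| Loss of after values | Starting from 34 per group | Starting from 40 per group |
|---|---|---|
| 0% | 34 left, 90.2% | 40 left, 94.2% |
| 10% | 30 left, 86.1% | 36 left, 91.7% |
| 15% | 28 left, 83.6% | 34 left, 90.2% |
| 20% | 27 left, 82.2% | 32 left, 88.3% |
| 25% | 25 left, 79.1% | 30 left, 86.1% |

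**Bias with no true effect.** Assumptions: 40 per group; about 21% loss in training, depending on the week-2 change; 5% loss in observation; 4,000 simulated trials. The completers contrast favoured training by 0.04, 0.07 and 0.10 SD under weak, moderate and stronger dependence. Imputing from baseline and week 2 left less than 0.01 SD.

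A hand check shows what these values require. If a fraction p is lost, the completers' mean minus the mean of all children equals p × (completers' mean − mean of those lost). With p = 0.21, a bias of 0.04 needs a gap of 0.04/0.21 = 0.19 SD, and 0.10 needs 0.10/0.21 = 0.48 SD. Relative to the planned 0.8, the bias is 0.04/0.8 = 5% to 0.10/0.8 = 12.5%.

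**What interim values add.** This is a separate illustration: true difference 0.8 SD, correlation 0.7 between adjacent weeks, 34 per group, roughly 20% loss after week 2, and poor responders to training more likely to leave. The mean estimates were:

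- complete data: 0.80
- completers: 1.03
- likelihood model on the two time points: 0.91
- likelihood model that also uses weekly values: 0.80

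The completers bias here is 1.03 − 0.80 = 0.23, larger than in the first set-up because the assumptions differ. In both set-ups loss depends on week-2 values that the better method can see, so the near-complete recovery is partly built in.

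**The case against.** The protocol nowhere says that incomplete children are deleted. That is how the classical procedure behaves. An imputation rule could sit in a statistical analysis plan that is not shown, so the absence of such a rule here is not a fault. This stands. What remains is that sections 13.2 and 13.3 fix a population and a method that, on their own, do not match.

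A reader might infer that every child who stops training is lost. Section 5.4 does not support that: it asks that dropouts still be evaluated, and a child who stops training but attends the final evaluation stays in the ANOVA. The problem concerns missing after values, not poor adherence.

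A reader might also infer that the ANOVA throws away recorded main-outcome data. That goes too far on three counts. Section 3.1 allows gait collection to stop after a pain report, so the protocol does not settle whether the angles exist. It is the after-minus-before definition in section 8.1 that leaves interim values out. Section 1.1 intends rehabilitation gait for the neural network models, so the values are unused in the efficacy comparison rather than discarded.

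Nor should a gain in precision from averaging four weekly values be claimed. A four-week average is a different quantity from the week-4 contrast.

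Finally, the dropout rates and their dependence on response are assumptions, so the bias figures are illustrative.

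**Conclusion.** The point holds as a mismatch between the analysis set and the named method. Followed as written and run in the classical way, the efficacy comparison is a completers analysis under a full-analysis-set label.

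The likely direction is in favour of training, by roughly 0.04 to 0.10 SD with about 21% against 5% loss. This rests on loss being greater among trained children who are not improving. If few after values are missing, or if loss is unrelated to response, the bias is small or absent and only power is affected. With equal groups of 40, power stays at 90% up to 15% loss.

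The benefit of interim sensor angles depends on their being collected, which the protocol leaves inconsistent. The change is still worth making, because section 13.3 can name a better-suited method in the same software.

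**What to change.** 1. **Push-off angle (13.3).** Replace repeated measures ANOVA with a likelihood-based linear mixed model (SPSS MIXED) with group, week, group × week and the pre-training value. Use weekly mean sensor angles where collected, include every child with any value after the start, and take the week-4 group contrast as the result. Report how many children in the full analysis set have no value after the start.
2. **Sensor data.** Reconcile section 3.1 with the procedure table and sections 1.1 and 8.1 on whether gait is recorded during the intervention weeks. Add the weekly angle to section 8.1.
3. **FPI-6.** Use a baseline-adjusted model and report how many children in the full analysis set lack the after value. With only two time points, multiple imputation from baseline alone adds little and is not needed.

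Cost: changes to the text of sections 3.1, 8.1 and 13.3, a defined weekly summary with a minimum-wear rule, and a little programming. The software stays the same. No new data are needed if the sensor is worn during training. If interim angles turn out not to be collected, a mixed model on two time points recovers only part of the loss (0.91 against a true 0.80 in the illustration, compared with 1.03 for completers).
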